3. STUDY DESIGN

3.1 Study Design

The trial will evaluate the safety and efficacy of 3 dose regimens of H-1337 (0.6% b.i.d., 1.0% b.i.d. and 1.0% q.a.m., and timolol maleate (0.5%, b.i.d.) OU for 28 days (\pm 2-day allowable window for Day 28).

Approximately 200 subjects will be randomized and dosed for 28 days. The parallel group, double-masked, active-controlled study will include the following dosing cohorts:

- H-1337 0.6% Ophthalmic Solution b.i.d. (n=50)
- H-1337 1.0% Ophthalmic Solution b.i.d. (n=50)
- H-1337 1.0% Ophthalmic Solution q.a.m. and H-1337 placebo q.p.m. (n=50)
- Timolol 0.5% Ophthalmic Solution b.i.d (n=50)

3.2 Randomization

H-1337 and its control (timolol) will be packaged in similar bottles which are concealed in identical packaging. An interactive web response system (IWRS) will be used for randomization.

3.3 Maintenance of Randomization Codes

The study will be double-masked to reduce potential bias in clinical assessments. Upon approval of D. Western Therapeutics, Inc., and prior to initiation of the study, an unmasked statistician will generate and maintain the randomization codes which are consistent with the study design.

Version Date: 19 Jan 2024

Other study statisticians will be masked to the identity of the treatments until all data have been entered into the database and locked.

In the case of an emergency only, if it is necessary for the investigator (or a treating physician) to know the treatment a subject is receiving, site personnel can complete the subject treatment breaking code procedure in IWRS. The mask should be broken only for safety purposes and only if knowing the drug allocation will have a direct impact on the subject's immediate medical management. If at all possible, the Medical Monitor should be contacted prior to emergency unmasking:

[name] [contact]
[contact]

If this is not possible and unmasking occurs without prior Medical Monitor approval, the Medical Monitor must be notified within 24 hrs. The circumstances leading to unmasking of each subject are to be promptly communicated via telephone and/or in writing to the sponsor (or sponsor's designee) and the IRB. Every effort should be made to keep the subject in the trial after the randomization code is broken until the completion of all visits.

3.4 Trial Treatment

Subjects will receive one of four dosing arms: H-1337 (0.6% b.i.d., 1.0% b.i.d. and 1.0% q.a.m. with H-1337 placebo q.p.m.), and timolol maleate (0.5%, b.i.d.) OU for 28 days . IP will be administered bilaterally throughout the trial.

The IWRS will assign a kit number to subjects who qualify for randomization. Each IP kit will contain 3 inner cartons. The first carton containing 2 pouches (each pouch containing 1 a.m. and 1 p.m. bottle) will be dispensed on Day 1 (Baseline). The second carton will be dispensed to the subject on Day 14. The third carton will serve as a back-up should the subject require a replacement carton.

3.5 Duration

Each subject's participation will consist of two phases: a Screening Phase (Screening and Baseline Visit 2 and Visit 3 Pre-T₀) where subjects will suspend dosing of any current ocular hypotensive therapy, and a Dosing Phase, starting on Day 1 after Pre-T₀. If a subject is not using ocular hypotensive therapy at Screening Visit 1, there is no applicable washout period and the Baseline Visit should occur within 1 to 42 days after Screening Visit 1.

A subject could participate in the study for a total of up to approximately 11 weeks. Subjects who meet the applicable inclusion/exclusion criteria at the Screening Visit will discontinue use of any current ocular hypotensive therapy during the washout period. (Note: At Investigator's discretion for subject's safety, initiation of a different IOP lowering therapy with a shorter washout period is permitted during a long washout period provided all appropriate washout periods are met prior to Visit 2.) The washout duration will be dependent on the subject's prestudy ocular hypotensive therapy. The table below lists the applicable washout durations for various pre-study ocular hypotensive medications. (Note: This table may not be inclusive of all

ocular hypotensive medications. The Medical Monitor should be contacted for further information regarding the washout period of an ocular hypotensive not included in the table.) If the Investigator assesses an acceptable risk, subjects may extend washout up to 49 days to accommodate scheduling.

 Table 2:
 Ocular Hypotensive Medication Washout Schedule

Ocular Hypotensive Generic/Trade Names	Washout period* (between Screening and Baseline Visit)
Muscarinic agonists (e.g., pilocarpine) and Oral or Topical Carbonic Anhydrase Inhibitors (CAI)	≥ 5 days
Beta-adrenoceptor antagonists	≥ 6 weeks
Alpha adrenoceptor agonists	≥ 5 weeks
Prostaglandin analogues, Combination Drugs (use longest wash-out period of individual components) *	≥6 weeks
Rho-associated protein kinase (ROCK) inhibitors	≥ 6 weeks

^{*}The washout period of longest duration should be used when the subject is taking multiple ocular hypotensive medications from more than one class. Additional +1 week extended washout permitted to accommodate scheduling considerations (Stroman et al., 1997; Johnson and Jampel, 2021).

Following the applicable washout period, the subject will return for applicable inclusion/exclusion evaluations on the Baseline Visit (Day 1) and a subject meeting all inclusion/exclusion criteria at $Pre-T_0$ will be randomized to IP. Both eyes will be dosed and evaluated for safety throughout the trial. The study eye is the eye that meets all entry criteria including the IOP criteria after washout. Should both eyes meet the criteria then the study eye will be defined as the eye with the higher $Pre-T_0$ 8 am IOP on Baseline (Day 1). If both eyes have the same $Pre-T_0$ 8 am IOP on Baseline (Day 1), the study eye will be the right eye.

Dosing will be initiated on Day 1 in the office after measurement of the $Pre-T_0 \ 8$ a.m. IOP and the completion of all examinations required prior to the $Pre-T_0 \ 8$ a.m. IOP measurement. The subject will be dosed for up to 28 days during which time they will be monitored for safety, tolerability, and efficacy assessments according to the Schedule of Study Assessments and Procedures.

The duration of participation for subjects in each stage will be as follows:

Screening Visit: 1 day

Washout Period: up to 42 days (+ 7 days) depending on pre-study ocular hypotensive therapy

Treatment Period: 28 days \pm 2 days

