4.1 Inclusion Criteria

- 1. 18 years of age or older.
- 2. Diagnosis of bilateral primary open angle glaucoma or ocular hypertension.
- 3. One qualifying IOP criteria after washout:
 - Baseline (Day 1) at T_0 ($T_0 = 8$ am ± 30 min [IOP time]) IOP ≥ 23 mmHg in the study eye.
- 4. IOP criteria after washout \leq 32 mmHg OU at all qualifying time points/visits.
- 5. Best-corrected visual acuity (BCVA) in both eyes of 20/200 or better on Snellen, equivalent to + 1.0 log Mar at Visit 1 Screening.
- 6. Able and willing to sign informed consent, follow study instructions and complete all study visits.
- 7. As applicable, must be willing to discontinue the use of all ocular hypotensive medication(s) in both eyes prior to receiving the study medication and for the entire course of the study.
- 8. Able to self-administer or have a caretaker administer investigational product eye drops.

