- 27. Clinically significant systemic, psychiatric or psychological disease (for example, renal, hepatic, uncontrolled diabetes, uncontrolled blood pressure, autoimmune disorders, psychiatric disorders, endocrine disorders, or any other disorders) or dependency which, in the investigator's judgment, would be unsafe and interfere with interpretation of the study results or the subject's ability to comply with the study requirements.
- 28. Contraindication to beta-blocker usage including: reactive airway disease, uncontrolled heart failure, or second as well as third degree cardiac block, myasthenia gravis.
- 29. Anticipated changes or initiation of medications which might affect IOP and/or systemic blood pressure within 7 days prior to Baseline/Day 1 (e.g., including, but not limited to: oral anti-hypertensives such as sympathomimetic agents, beta-adrenergic blocking agents, alpha agonists, alpha adrenergic blocking agents, calcium channel blockers, angiotensin converting enzyme inhibitors [diuretics are allowed]), and 2 months prior to Baseline/Day 1 for corticosteroids (i.e., oral, nasal, topical [dermal, mucosal], and/or inhaled corticosteroids). If there are no further anticipated changes in medications that could affect IOP and/or systemic blood pressure, then once the subject is stable on their new dose of medication for the required time period, the subject may complete the Baseline Visit, assuming that all other screening requirements are met. Medications used on an adjustable or sliding scale based on testing results are allowed. Note: Vaccines are permitted.
- 30. Women of childbearing potential who are pregnant, nursing, planning a pregnancy, or not using a medically acceptable form of birth control. An adult woman is considered to be of

childbearing potential unless she is one year post-menopausal or three months post-surgical sterilization. All females of childbearing potential must have a negative urine pregnancy test result at the Screening Visit and at Baseline (Day 1) prior to randomization in the study and must not intend to become pregnant during the study.

- 31. History of drug or alcohol abuse within the last 5 years.
- 32. Unwillingness to refrain from consumption of alcohol or cannabinoids, including tetrahydrocannabinol (THC) and cannabidiol (CBD), in any form by any delivery route, on the day prior to each study visit after Visit 1 Screening.
- 33. Related to site study staff and/or site employees.

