5. STUDY VISIT PROCEDURES

All study visit procedures should be conducted in the order listed in Section 5.1.

Informed Consent: Properly executed informed consent (written and verbal) is to be obtained prior to completion of any study-related procedures. Subjects must review, sign, and date the informed consent document and receive a copy. The original document should be retained in the Investigator's Site File (ISF) or with the Subject's source documents.

Medical and Ocular History: Relevant and clinically significant medical and ocular history must be recorded. This includes reported changes between Screening Visit 1 and first IP administration.

Concomitant Medications/Procedures: All prescription and over-the-counter (OTC) medications and nutritional supplements taken during the study and 30 days prior to the Screening Visit will be recorded. Additionally, all ocular hypotensive medications taken within 45 days prior to the Screening Visit will be recorded. Diagnostic and anesthetic eye drops do not need to be recorded. All procedures occurring during the study and 30 days prior to the Screening Visit will be recorded.

Randomization: Randomization will be accomplished using an Interactive Web Response System (IWRS). Site personnel will receive instruction about IWRS access and use.

Adverse Events: Any events occurring after the first dose of IP will be recorded as an adverse event. At each visit, the subject should be asked questions such as, "How are you feeling? How are your eyes feeling today? Have you had any changes since the last exam?"

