4.1 Definitions and Conventions

Listings present the subjects individual data, while summary tables present the summary statistics of subjects data.

Summary statistics will be presented for continuous variables, by way of n, mean, standard deviation (SD), median, minimum and maximum. For categorical variables including binary variables, frequency counts and percentages will be presented. Percentages will be calculated using the total number of subjects per treatment groups or the total number of subjects with an assessment per treatment groups, depending on the nature of the analysis.

In addition, 95% 2-sided confidence intervals (CIs) will be presented, where relevant. In case of percentages, the CI will be computed using the Clopper-Pearson method. The CI will be computed for continuous variables using a t-test analysis.

Summary statistics will be displayed by treatment groups, which will be labelled as follow:

- Group 1: H-1337 0.6%
- Group 2: H-1337 1.0% b.i.d
- Group 3: H-1337 1.0% q.a.m
- Group 4: Timolol 0.5%

Baseline Value is defined as the last non-missing value prior to the first IP administration for vital signs, BCVA, biomicroscopy and dilated ophthalmoscopy (Day 1 Pre- T_0 for vital signs, BCVA and biomicroscopy; Screening for dilated ophthalmoscopy). For IOP and conjunctival hyperemia grading, time-matched baseline values are defined at Pre- T_0 on Day 1 (Visit 3), T_0 +2 hours, T_0 +4 hours, T_0 +8 hours and T_0 +12 hours on Day 0 (Visit 2). For mean diurnal IOP, baseline is defined at Day 0.

Change from Baseline is defined as the difference in value of the assessment between the considered visit and the baseline value. In the case of IOP and conjunctival hyperemia grading, change from Baseline is the difference in value of the assessment between the considered visit at a particular timepoint and the corresponding baseline value.

Study eye is defined as the eye that meets all entry criteria including the IOP criteria after washout. Should both eyes meet the criteria then the study eye will be the eye with the higher 8 am IOP at Baseline (Day 1). If both eyes have the same 8 am IOP at Baseline (Day 1), the study eye will be the right eye.

SAS® version 9.4 or above will be used to perform the analyses.

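### A subject off treatment at Screening skips washout, with no minimum time since the last dose

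*Protocol*

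**What the plan says.** Protocol Section 3.5 sets washout by what the subject is taking at one visit: "If a subject is not using ocular hypotensive therapy at Screening Visit 1, there is no applicable washout period". For these subjects "the Baseline Visit should occur within 1 to 42 days after Screening Visit 1".

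Table 2 in the same section requires at least 6 weeks for beta-blockers, prostaglandin analogues, combination drugs with such a component, and ROCK inhibitors. It requires at least 5 weeks for alpha agonists, and at least 5 days for muscarinic agonists and carbonic anhydrase inhibitors. Its clock runs "between Screening and Baseline Visit", so it presumes that the drug is still in use at Screening. The text introducing it is wider and speaks of "applicable washout durations for various pre-study ocular hypotensive medications".

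Three other provisions bear on the point:
- Section 5 states that "all ocular hypotensive medications taken within 45 days prior to the Screening Visit will be recorded".
- Exclusion 29 covers "Anticipated changes or initiation of medications which might affect IOP and/or systemic blood pressure within 7 days prior to Baseline/Day 1".
- Inclusion 3 ("One qualifying IOP criteria after washout") requires at least 23 mmHg in the study eye at Day 1 T0, and inclusion 4 caps IOP at 32 mmHg.

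On the analysis side, SAP Section 4.1 takes the Pre-T0 baseline from Day 1 and the baselines for the later hours from Day 0 (Visit 2). SAP Section 4.5 lists washout information and does nothing further with it.

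**The concern.** The sponsor has judged that these drug classes need 5 to 6 weeks to clear. The exemption drops that requirement for anyone who happens to be off treatment at Screening, however recently they stopped. Such a subject may reach Baseline with IOP still partly lowered by the old drug. As that effect fades over the 28 days, the change from baseline at Day 28 understates what the study drug did. Because only some subjects are affected, the spread of the changes also grows. What is at stake is a diluted Day 28 change within each arm and a slightly wider confidence interval for the non-inferiority comparison.

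**Working it through.** **1. Off-drug time that the text permits.** Let *d* be the days from last dose to Screening and *b* the days from Screening to Baseline (1 to 42). Off-drug time at Baseline is *d + b*.

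| *d* | *b* | Days off | Short of 42 | Short of 35 |
|---|---|---|---|---|
| 1 | 1 | 2 | 40 | 33 |
| 1 | 2 | 3 | 39 | 32 |
| 7 | 1 | 8 | 34 | 27 |
| 1 | 41 | 42 | 0 | 0 |
| 41 | 1 | 42 | 0 | 0 |

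The rows with *b* = 1 need Screening and Visit 2 on the same day. If Visit 2 has its own day, add one day to the days off.

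**2. Whether another rule supplies the interval.** None does.
- Inclusion 7 asks for willingness to discontinue and sets no drug-free time.
- Exclusion 29 reaches back 7 days, and its examples are systemic drugs. Read broadly, it gives a floor of about 7 days, still 35 short of 42.
- The notes in Section 3.5 and exclusion 17 on meeting washout before Visit 2 concern subjects switched to another therapy.
- The 45-day record feeds no eligibility or scheduling rule.

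**3. The plan's own power figure.** Protocol Section 8.1 and SAP Section 3.3 use 45 per arm, a 2 mmHg limit (magnitude), SD 3.0 and one-sided alpha 0.05. The noncentrality is 2 / (3 × √(2/45)) = 3.162. The noncentral t on 88 df gives 93.2%, which agrees with the stated 90% or more.

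**4. Size of the effect.** The documents give no prevalence or residual, so these inputs are assumptions:
- a fraction *p* = 5–10% of screened subjects carries a residual *r* = 3–4 mmHg at baseline, gone by Day 28;
- off-drug IOP *X* is normal with mean μ = 23–27 and SD 3 mmHg;
- SD of change is 3.0 without such subjects.

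A subject with residual *r* shows *X − r* on Day 1, so must have *X* between 23 + *r* and 32 + *r* to enter. With *q*₀ = P(23 ≤ *X* ≤ 32) and *q*₁ = P(23 + *r* ≤ *X* ≤ 32 + *r*):

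- share among randomised: *s* = *p q*₁ / (*p q*₁ + (1 − *p*) *q*₀)
- dilution of the mean Day 28 change: *s r*
- SD = √(9 + *s*(1 − *s*) *r*²)

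The extremes are:
- μ = 23, *p* = 0.05, *r* = 4: *q*₀ = 0.499, *q*₁ = 0.091, *s* = 0.0095, dilution 0.04 mmHg.
- μ = 23, *p* = 0.05, *r* = 3: *s* = 0.0165, the lowest SD, 3.02.
- μ = 27, *p* = 0.10, *r* = 3: *q*₀ = 0.861, *q*₁ = 0.627, *s* = 0.075, the largest share.
- μ = 27, *p* = 0.10, *r* = 4: *q*₁ = 0.499, *s* = 0.0605, dilution 0.24 mmHg, SD = √(9 + 0.0605 × 0.9395 × 16) = 3.15.

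| | No residual | With residual |
|---|---|---|
| Share of randomised | 0 | 1.0–7.5% |
| Dilution at Day 28, each arm (mmHg) | 0 | 0.04–0.24 |
| SD of change (mmHg) | 3.00 | 3.02–3.15 |
| 95% CI half-width, 50 per arm (mmHg) | 1.19 | 1.20–1.25 |
| Power, plan's stated inputs | 93.2% | 92.9–91.1% |
| Power per time point, margin 1.5, two-sided 95% CI, 50 per arm, true difference 0 | 69.7% | 69.0–65.5% |

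The half-width is *t*(0.975, 98 df) × SD × √(2/50). The last row uses the margin and interval of Protocol Section 8.4 and SAP Section 4.3, with a true difference of zero as a further assumption. Ignoring the entry limits, the upper case is 0.10 × 4 = 0.40 mmHg, SD √(9 + 0.09 × 16) = 3.23 and power 89.8% on the stated inputs.

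**The case against.** The best defence is one of intent. Section 3.5 ties washout to pre-study therapy more than once, so not using may have been meant as untreated. The 45-day look-back for hypotensives, against 30 days for other drugs, sits just above the longest Table 2 interval and looks designed to check washout. That reading is plausible. But the exemption sentence is explicit, its key term is undefined, and nothing connects the record to eligibility, so sites could apply it differently.

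The second line is that the effect is small and its inputs are unsupported. Much of this stands:
- Nothing in the documents shows that anyone stopped treatment shortly before Screening.
- Baseline may fall up to 42 days after Screening, by when the residual may have gone. With a 1–2 mmHg residual the same formulas give SD 3.01–3.05 and power 93.1–92.5% on the stated inputs.
- Adjustment for baseline shrinks the effect further.
- The Day 1 time points are hardly touched, because their baseline is only 1 to 4 days earlier. The dilution concerns Day 28.

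One qualification runs the other way. The 23 mmHg minimum applies only at Day 1 T0. The later-hour baselines come from Day 0, which has no minimum and lies closer to the last dose.

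**Conclusion.** The concern holds, at low severity. As written, Section 3.5 lets a subject reach Baseline within days of stopping a drug for which Table 2 requires 5 to 6 weeks, and no other rule closes the gap. The arms are randomised, so the mean shift largely cancels from H-1337 minus timolol in expectation. What remains is a Day 28 change diluted within each arm and a confidence interval wider by roughly 0.01 to 0.06 mmHg on each side. These sizes rest wholly on the assumed prevalence, residual and off-drug IOP distribution, and take no credit for baseline adjustment. Within the entry limits, power on the plan's stated inputs stays above 90% throughout the assumed range.

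**What to change.** In Section 3.5, apply the exemption only when the Table 2 interval since the last dose of every hypotensive in the 45-day record will have elapsed by Baseline. Otherwise delay Baseline until it has. The Table 2 intervals themselves need no change.

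The cost is one sentence and a check on data already collected. Since Baseline is at least 1 day after Screening, any dose within 42 days of Baseline falls at most 41 days before Screening, inside the 45-day look-back. The longest wait after Screening is 42 − *d*, at most 41 days, which fits the existing 1 to 42 day window. The downside is that a few recently untreated subjects wait longer, off therapy, before randomisation.

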3.6 Drug Packaging and Labeling

H-1337 and timolol 5 mL low density polyethylene (LDPE) bottles will be similar but not identical. Each bottle will be concealed in an identical foil pouch. Each identical IP kit will contain 3 identical inner cartons, each containing 2 identical foil pouches (one a.m. and one p.m. pouch). The kits, inner cartons, pouches and bottles will be labeled in a format appropriate for the study.

Masking will be maintained by the appointment of an unmasked study coordinator not

participating in key endpoint data collection at each clinical site, solely responsible for subject IP dispensation and return.

3.7 Drug Accountability and Storage

All IP required for this study will be provided by D. Western Therapeutics, Inc., or its designee. The recipient will acknowledge receipt of IP, indicating shipment content and condition. Damaged supplies may be replaced upon notification to D. Western Therapeutics, Inc., or its designee. Accurate records of all IP dispensed from and returned to the study site should be maintained and recorded. A study monitor will periodically check the supplies of IP held at the site to verify accountability of all IP. All used and unused IP (non-dispensed) will be returned to D. Western Therapeutics, Inc., or its designee.

IP must be stored in a temperature monitored secure and restricted storage area with limited access. Temperature monitoring records must be maintained throughout the trial. IP should be stored at controlled refrigerated temperatures from 2° - 8° C and protected from light. Once dispensed to subjects IP bottles may be stored at room temperature, i.e., 15° - 25° C. Subjects must be instructed not to leave the IP in their car, near a window, or outdoors where it may be exposed to direct sunlight and/or heat for a prolonged period.

The IP must not be used outside the context of this protocol. Under no circumstances should the investigator or site personnel supply IP to other clinical sites, investigators or subjects, or allow the IP to be used other than as directed by this protocol without prior authorization from D. Western Therapeutics, Inc.

